5.3 Level of significance

In general, whole brain statistical analyses will be performed with rigorous control of false positive rates using cluster-based methods (Worsley, Evans, Marrett, & Neelin, 1992). This substantially increases the reproducibility of findings relative to region-of-interest type approaches. Statistical significance will be defined by $p<0.05$.

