IDENTIFYING MARKERS OF TRAJECTORY IN PEDIATRIC COMPLEX REGIONAL PAIN SYNDROME

PROTOCOL

Principal Investigators:

[name]

Date: July 12, 2018

SYNOPSIS

Title	Identifying markers of trajectory of short-term and long-term recovery in pediatric complex regional pain syndrome (CRPS)
Study Objectives	Characterize neurological and psychosocial markers of trajectory of recovery in pediatric CRPS.
Significance	
 1. CRPS is a severe and complex chronic pain condition in children. 2. Many psychosocial factors impact its development and recovery. 3. CRPS has a strong central component, which is reflected by structural and functional changes in the brain. 4. The interaction between these cerebral changes and recovery has been seldom investigated to date. 5. Interactions between cerebral changes and psychosocial factors, which might affect recovery, are unknown.
Study Design	Basic science investigation of children with CRPS undergoing outpatient and inpatient treatments at CCHMC and of healthy children.
Primary Aim	To characterize markers that are predictive of trajectory of recovery in CRPS patients
Sample size	63 youth/parent dyads
Study Duration	Two years of data acquisition, unlimited analyses
Inclusion Criteria	
All Children:
 
 – Age between 10 and 17 years old – Fluent in English

Inpatients:

- Diagnosis of CRPS
- Former unsuccessful treatment for CRPS
- Scheduled for or beginning the usual inpatient treatment for CRPS at the FIRST clinic at CCHMC.

Outpatients:

- Diagnosis of CRPS
- Scheduled for or beginning the usual outpatient treatment for CRPS at the pain management clinic

Healthy children:

- No diagnosis of chronic pain.

Parents:

- Fluent in English
- Child participating in the study

Exclusion criteria

All child participants:

- Weight/size incompatible with MRI scanner
- Identification of brain, neurologic, or severe psychiatric abnormalities beyond those normally associated with chronic pain.
- Documented developmental delays or impairment
- Any MRI contra-indication, including
 - Braces, stents, clips, pace-maker or other metal implants affecting the safety of the participants in the scanner and/or the quality of the images
 - pregnancy
 - claustrophobia

TABLE OF CONTENTS

1	SPECIFIC AIMS	6
1.1	SPECIFIC AIM 1	6
1.2	SPECIFIC AIM 2	7
1.3	SPECIFIC AIM 3	7
2	BACKGROUND INFORMATION	7
2.1	BACKGROUND	7
2.2	PRIOR STUDIES	9

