Pediatric Complex Regional Pain Syndrome (CRPS) is a severe and complex type of pediatric chronic pain, which impacts majorly the children's and their families' lives (McClain & Suresh, 2011). CRPS is divided into Type I and Type II, which are differentiated by the absence (Type I) or presence of a discreet nerve injury (Type II) (Harden et al., 2010). CRPS is treated, in the first instance, with outpatient multidisciplinary interventions (Carter & Threlkeld, 2012; Dickson, 2017; Katholi, Daghstani, Banez, & Brady, 2014; Maihöfner, Seifert, & Markovic, 2010). However, several psychosocial factors, such as pain catastrophizing, depression, and/or familial environment, can affect pain symptoms and recovery (Bruehl & Chung, 2006; Cruz, O'Reilly, Slomine, & Salorio, 2011; Vervoort, Trost, & Van Ryckeghem, 2013). In such cases, more intensive interventions necessitating hospitalization are necessary to help the patients (Dickson, 2017). Defining which factors predict the trajectory of recovery could allow for better targeting of the treatment that a patient needs to successfully recover. In this study, the effect of psychosocial and sensory factors and possible brain markers predicting changes in pain symptoms before – after treatment will be investigated in children diagnosed with CRPS and currently undergoing the usual inpatient or outpatient treatment at CCHMC. In addition, brain changes before – after treatment will be analyzed, as well as potential psychosocial influences on these changes. To establish a baseline of changes associated with CRPS recovery, potential psychosocial and sensory markers, as well as brain activation and connectivity in CRPS patients will be compared to healthy children. To assess the psychosocial environment, parents of children enrolled in the study will complete a series of questionnaires.

For this purpose, we define the following specific aims to investigate in a main study:

1.1 Specific aim 1

Identify changes in psychosocial, psychophysical, sensory, and cerebral characteristics associated with CRPS.

Psychosocial, psychophysical, sensory, and cerebral measurements in children diagnosed with CRPS will be compared with such measurements in healthy children before or at the beginning of an inpatient or outpatient treatment at CCHMC.

We hypothesize that children diagnosed with CRPS will differ from healthy children in their responses to psychosocial, psychophysical, sensory, and cerebral measurements.

1.2 Specific aim 2

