Develop predictors of short-term and long-term recovery from CRPS using psychosocial measures, sensory sensitivity, and brain function and structure.

Changes in symptoms of CRPS, such as pain and functional disabilities, will be investigated in relation to potential psychosocial, sensory, and brain markers. Variables obtained at baseline will be examined for significant relationship with recovery.

1.3 Specific aim 3

Investigate the evolution of changes in psychosocial, psychophysical, sensory, and cerebral measures, associated with CRPS.

Short-term and long-term changes in psychosocial, psychophysical, sensory and cerebral measures in children diagnosed with CRPS will be compared to changes in healthy children.

We hypothesize that differences in psychosocial, psychophysical, sensory and cerebral measures between children with CRPS and healthy children will be reduced immediately after treatment, as well as six-month post treatment.

2 Background information

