3.1 Overview

This is a basic science investigation of potential psychosocial, sensory, and brain markers predicting trajectory of short-term and long-term recovery in pediatric CRPS following both inpatient and outpatient treatment.

The usual inpatient treatment lasts on average three weeks and includes physical, occupational, and recreational therapy, as well as psychotherapy, while patients keep their regular pharmacological treatment. The usual outpatient treatment lasts on average several months and includes physical therapy and psychotherapy, in addition to pharmacotherapy. For both inpatients and outpatients, the primary anti-neuropathic pharmacotherapy typically includes gabapentin, pregabalin, or amitriptyline, or, less frequently, duloxetine. It is important to note

that this study is not designed to investigate the efficacy of treatment *per se*, instead it aims to predict trajectory during the course of treatment as usual. This study is primarily mechanistic and does not include any intervention or modification of treatments. Therefore, patients, who are scheduled for regular inpatient or outpatient treatment of CRPS, are free to refuse to enroll without any consequences for the scheduled treatment.

The investigated markers will be assessed in patients undergoing inpatient or outpatient treatments. To define potentially relevant markers, measurements in patients will be compared to the same measurements in healthy children. For this purpose, participants will undergo a testing session just before the beginning of their treatment or as close as possible from the beginning of their treatment.

To establish the influence of potential markers on short-term recovery, patients will undergo an additional session upon completion of their treatment. To investigate the effect of the previously defined markers on long-term recovery, patients will complete a third session at six months after treatment. For comparison purposes, healthy control children will undergo sessions following the same schedule as the patients. To assess the association between symptoms of CRPS in children and social environment, at least one parent of each enrolled child will be asked to complete three sessions following the same schedule as their child.

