3.4.3 Behavioral and clinical measures

Participants to the study might be asked to complete the following behavioral and clinical measures.

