5.1.2 Analyses of behavioral and psychophysical data

Questionnaires data will be scored and used to characterize patients-control differences and serve as potential covariates in current and future analyses.

The effect of behavioral factors on the trajectory of our outcome measures, i.e. changes in pain ratings, in functional disabilities over time, and brain function and structure, might be assessed by multilevel regressions and mixed ANOVAs. Post-hoc analyses will be performed when appropriate.

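### Aim 2's questionnaire and sensory markers have no multiplicity control: each is judged at p<0.05, so 0.85–1.40 false predictors are expected per outcome and time point if 17–28 markers are tested and none is real

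*Combined protocol and SAP*

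**What the plan says.** The synopsis gives the Primary Aim as "To characterize markers that are predictive of trajectory of recovery in CRPS patients". Section 1.2 (Aim 2) puts this into practice as "Variables obtained at baseline will be examined for significant relationship with recovery", for both short-term and long-term recovery, with pain and functional disability named as examples of symptoms.

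Section 5.3 says that "whole brain statistical analyses will be performed with rigorous control of false positive rates using cluster-based methods". Its general criterion is "Statistical significance will be defined by $p<0.05", with no adjustment for the number of tests.

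Section 5.1.2, which covers the behavioral and psychophysical data, says that the effect of behavioral factors on "changes in pain ratings, in functional disabilities over time, and brain function and structure, might be assessed by multilevel regressions and mixed ANOVAs", with post-hoc analyses where appropriate. It names no correction, marker list, lead outcome or validation step.

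Section 3.1 describes a preliminary comparison: "To define potentially relevant markers, measurements in patients will be compared to the same measurements in healthy children". It gives no cut-off and no error rate for that step.

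**The concern.** Aim 2 relates a long list of baseline measures to recovery and looks for significance. Imaging has a stated defence against testing many things at once. The questionnaires and sensory tests have none: a marker that reaches p<0.05 meets the plan's only criterion, however many others were tried beside it.

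This bears on the main conclusion. Section 1 says "Defining which factors predict the trajectory of recovery could allow for better targeting of the treatment that a patient needs to successfully recover". A marker that passed by chance would be reported in the same terms as a real one, and the plan has no rule to tell them apart.

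**Working it through.** **Inputs**

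- Level per test: 0.05 (section 5.3).
- Questionnaires: section 3.2.4.2 lists 9 for children and 9 for parents. The FDI is an outcome, so 18 − 1 = 17 markers.
- Sensory measures, one value per test in section 3.4.4.2: tactile and vibration thresholds (2), thermal thresholds (4), suprathreshold heat and cold (2), cold tolerance (1), offset analgesia (1), conditioned pain modulation (1). That is 11, and 17 + 11 = 28.
- Patients: section 5.2 has 18 per group before the allowance for incomplete data. 18 × 1.15 = 20.7, rounded up to 21, and 3 × 21 = 63, so the plan's total reproduces. The two CRPS groups give 2 × 21 = 42 patients, or 2 × 18 = 36 if the allowance is used up.

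The range of 17–28 is an assumption. It could be lower: section 3.4.3 says "Participants to the study might be asked to complete the following behavioral and clinical measures", and the PSOCQ-A may not be given to younger children. It could be higher: child PROMIS covers three domains and parent PROMIS two, the PSAQ has two subscales, and sensory testing covers two limbs.

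**Expected false predictors, one outcome at one time point, no real effects**

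Expected number = markers × 0.05. Expectations add whether or not the tests are correlated.

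- 17 × 0.05 = 0.85
- 28 × 0.05 = 1.40

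Simulated means agreed at every marker correlation tried. A joint regression with one coefficient test per marker has the same expectation.

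**Chance of at least one**

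For independent tests it is 1 − 0.95^k: 1 − 0.95^17 = 58% and 1 − 0.95^28 = 76%. Correlated markers need simulation (null data, 42 patients, equal correlation between markers). Values are approximate, to a point or two of simulation error.

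| Marker correlation (assumed) | 17 markers | 28 markers |
|---|---|---|
| 0 | 59% | 77% |
| 0.5 | 40% | 50% |
| 0.6 | 32% | 42% |
| 0.7 | 29% | 34% |

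With Benjamini-Hochberg at 5% across the markers, the chance was at or below about 5%.

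**What correction costs**

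If one marker is real, Benjamini-Hochberg is close to testing it at 0.05/k. The smallest significant correlation is r = t/√(n − 2 + t²), where t is the two-sided critical value on n − 2 degrees of freedom. Power is for a true r of 0.4.

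| Patients | Level | Smallest significant r | Power |
|---|---|---|---|
| 42 | 0.05 | 0.304 | 76% |
| 42 | 0.05/28 | 0.468 | 31% |
| 36 | 0.05 | 0.329 | 69% |
| 36 | 0.05/28 | 0.503 | 24% |

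With 17 markers, power at 0.05/17 is 37% with 42 patients and 29% with 36.

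**The case against.** The best defence is that this is discovery work. Aims 1 and 3 state hypotheses and Aim 2 does not. Section 3.1 calls the study mechanistic and excludes any change to treatment, and section 5.1.2 says only what might be done. With about 40 patients, strict correction would hide most moderate associations, as the power figures show. Much of this stands, and it is why mandatory correction alone would be hard to insist on. It does not remove the gap. No section calls Aim 2 exploratory, it is the Primary Aim, and it is framed around significance.

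A second defence is that the comparison with healthy children in section 3.1 screens the markers. It has no stated cut-off or error control, and the PSOCQ-P is for parents of patients only (section 3.4.3.3), so it has no control data.

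Three stronger readings are tempting, and the documents do not support them:

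- A reader might infer that there is no false-positive control at all. There is: p<0.05 limits the error of each single test, and imaging has its cluster-based rule. What is missing is control across the questionnaire and sensory markers.
- A reader might take one range for the chance of a false predictor as a bound. It moves with a marker correlation that the documents never give.
- A reader might multiply up over several outcomes and both horizons to a study-wide total. Neither the number of outcomes nor the tests per marker is fixed, so such a total would rest on the reader's own choices.

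**Conclusion.** The point holds as a gap in multiplicity control, confined to Aim 2's questionnaire and sensory markers. Its firm size is 0.85–1.40 expected false predictors per outcome and time point. That rests on three assumptions: 17–28 markers, one test of each, and no real effects. It does not rest on independence. The chance of at least one runs from about 29% (17 markers correlated at 0.7) to about 77% (28 independent markers) over the settings tried.

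The omission itself is plain from the text; the figures are illustrative. It affects what the study may conclude on its Primary Aim, not safety or data collection.

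**What to change.** Add an Aim 2 rule to section 5.3. Either route is acceptable, provided that the sponsor chooses before analysis.

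(a) **Confirm.** Name one lead recovery outcome and horizon, and list the baseline questionnaire and sensory markers. Apply Benjamini-Hochberg at 5% across that list. Report all other associations as exploratory, with estimates and unadjusted p-values.

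(b) **Explore.** Label Aim 2 exploratory. Report every test with unadjusted and Benjamini-Hochberg-adjusted p-values. Declare no marker a predictor on unadjusted p<0.05 alone.

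Under both, report any multi-marker model by its cross-validated performance, with marker selection carried out inside the folds. Brain markers stay under the existing cluster-based rule.

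The cost is SAP wording and a little analysis work; no further participants are needed. Route (a) also loses the power shown above, though less if several markers are real. Route (b) loses no power but supports no confirmed predictor.

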5.4 Participants to be included in the analyses

All participants whose data passes quality assurance (i.e. no MRI artifacts, no excessive movement, no reconstruction errors) will be included in analyses. Many analyses will be executed on a condition-by-condition basis. Thus, every effort will be made to include participants who have partially complete datasets but have successfully completed scans for a given condition.

6 Data management

An Electronic Data Capture (EDC) system that is designed to support reliable and secure entry of non-imaging data will be used for the study. Paper forms might be used for recording of pain ratings and may be used as backups for questionnaires in the event of computer malfunction during data acquisition.

6.1 Data Entry

Data can be entered directly via a fully validated and 21 CFR Part 11 compliant, secure application and stored centrally. Data will be entered by subject study identification number; names will not be linked with participant data in the database.

6.2 Data Validation and Monitoring

Real-time validations will be integrated into the data entry system. Inconsistent or questionable values can be flagged during entry, and reports can be automatically generated to the data entry client. These reports provide the information necessary to investigate any data entry errors or resolved questions regarding out-of-range or questionable values.

6.3 Data Security and Integrity

All data changes are written to an audit trail. The audit trail identifies the data item by table, column and key field. The entry includes the user, date and time, as well as the old value and new value. Data are saved at regular intervals during data entry to prevent loss of information in the event of a disruption of the Internet connection.

The following levels of security are employed to ensure privacy and integrity of the study data:

1. Access to the study data and protocol requires use of assigned user names and passwords.
2. Individual roles and access levels are assigned by the study data manager.
3. Passwords are changed regularly.
4. Web-based entry uses secure socket layer data encryption.
5. Data with identifiers will not be stored on laptop computers.

7 Ethics and human participants consideration

7.1 Potential Risks and Minimization of Risk

7.1.1 Potential risks associated with MRI Scanning

There are no adverse effects identified to date from undergoing functional imaging studies with MRI. Potential risks from MRI are addressed in the guidelines for the operation of clinical MR systems by the FDA in 2014¹.

- Main Static Magnetic Field: The 3.0 Tesla static magnetic field strength of the MRI scanners to be used in this study is below the 8.0 Tesla limit recommended by the FDA guidelines for human research. The FDA has concluded that magnetic field below 8.0 Tesla does not by itself impose a risk to human participants.

¹ <http://www.fda.gov/medicaldevices/deviceregulationandguidance/guidancedocuments/ucm072686.htm>

- Specific Absorption Rate: The FDA guidelines for the specific radiofrequency absorption rate (SAR) are set by limiting the patient's core temperature rise to less than 1 degree Celsius. In the absence of core temperature monitoring equipment, the recommended FDA limits for the head are 3.2 W/kg, on average. The MRI scanner system limits the SAR to 3.2 W/kg. In the event that this value is exceeded, the transmitter power supply is turned off automatically within 3 to 5 seconds. These measures ensure that the MRI scanner is well within the current FDA regulations on SAR.
- Gradient Speed: The FDA suggested rate of change of magnetic field (dB/dt) is based only on avoiding discomfort to the participant. Peripheral nerve stimulation and other symptoms do not usually occur until $dB/dt > 20T/sec$, and all sequences will be designed to avoid generation of such symptoms.
- Acoustic Noise: The FDA deems risks from scanner noise significant when the peak unweighted sound pressure level exceeds 140 dB or when the A-weighted root mean square (rms) sound pressure level is greater than 99 dBA with hearing protection in place. Hearing protection will be accomplished with our MRI compatible A/V system headphones. These specially designed headphones provide up to 30 dB of sound isolation from the MRI scanner, and will ensure that scanner noise levels do not pose any risk to hearing.
- Claustrophobia within the MRI Scanner: Healthy participants will be queried for claustrophobia and excluded. On occasion, a participant may be unaware of their claustrophobia until they are in the scanner. Since this is a basic research investigation, participants unable to tolerate the scan will simply be removed from the scanner. In addition, participants will be given a “panic” button to hold during the scans. In the event that a participant becomes uncomfortable, he or she can press the panic button to notify the operator of the need for immediate attention. Intercom contact will be opened immediately, and the participant can be removed from the scanner if needed. In addition, participants will be monitored visually and via microphone during the whole procedure to ensure that they are tolerating it.
- MRI Incompatible Objects in/on the Participant: MRI incompatible objects in/on the body have the potential to move, heat, and/or malfunction. Participants with MRI incompatible

objects within or on their body will be excluded from the study. Participants will be carefully screened before entry into the experiment and before entry into the scanner environment to minimize this risk.

7.1.2 Potential risks associated with psychological discomfort

Completion of psychosocial measures, aka questionnaires, may feel intrusive and uncomfortable to some persons. This might induce some mild psychological distress. If participants or their parents experience such feeling, they will be instructed to inform the experimenter, as stipulated in the consent/assent forms. In addition, they will be advised to contact the PI of this study. If necessary, they will be referred to a clinical psychologist for follow-up.

7.1.3 Potential risks associated with the sensory tasks

The sensory tasks include auditory, visual, and sensorimotor stimuli. Some of these stimuli might feel unpleasant to the participants, especially for patients who might experience hypersensitivity to sensory stimuli. These stimuli will be defined to remain below damaging thresholds.

7.1.4 Potential risks associated with quantitative sensory testing

Participants with chronic pain may experience exacerbations of their pain by the stimuli used during quantitative sensory testing. Stimulation paradigms will prioritize threshold level stimuli, and suprathreshold stimuli will be carefully tailored to each individual patient to minimize exacerbation of pain.

Thermal stimulators and/or water baths will deliver noxious and non-noxious thermal stimuli for the quantitative sensory testing. Noxious thermal stimuli have been repeatedly demonstrated to produce reliable changes in brain activity that can be detected with fMRI. Individual stimuli will range from 0° to 50°C to encompass both heat and cold pain. Heat stimuli will typically be applied to the skin of the arms, legs, or other body regions in an intermittent manner with combinations of areas and durations that eliminate the possibility of tissue damage. Stimuli in this temperature range have been used extensively by our laboratory and a number of different laboratories around the world and do not produce tissue damage, burns, or frostbite. Temperatures in this

range are frequently encountered in daily life (snow, ice water bath, handwashing, dishwashing etc.) and have been determined to not represent more than a minimal risk in other protocols at Cincinnati Children's Hospital.

As with any electrical device, there is a remote possibility that a stimulator malfunction could cause a burn. To minimize this risk, stimulators have fail-safe circuits to prevent excessive delivery of energy. Furthermore, all participants will be conscious, will not have any analgesic medications, and will be free to terminate the stimulus at any time. To facilitate escape from stimulation, probes will never be strapped to the participant. Instead, probes will be either manually applied by the study staff, held in place by a spring-loaded device, or applied by having the participants passively rest their limb in contact with the probe. Thus, the participants will only have to move their body part away from the probe in order to escape the stimulus.

